### **7.3 Supportive Care**

All supportive measures consistent with optimal patient care will be given throughout the study.

## 8 STUDY CALENDAR

1 cycle = 28 days ( $\pm$  3 days)

Examination	Screening 	C1D1 	C(2+)D1 	PSA Progression Confirmation 	End of Treatment 	Follow-up 
Informed consent	X					
Treatment after PSA Progression ICF 				X		
Medical history	X					
Eligibility criteria 	X					
Vital signs	X	X	X	X	X	
Physical examination	X	X	X	X	X	
ECOG performance status	X	X	X	X	X	
Hematology 	X	X	X	X	X	
Chemistry 	X	X	X	X	X	
Lipid Panel 	X	X	X	X	X	
PSA 	X	X	X	X	X	X 
Urinalysis	X					
Coagulation Panel 	X					
Testosterone	X 					
ECG	X					
Adverse Event Assessment		X	X	X	X	
Concomitant Medication Review	X	X	X	X	X	
CT scans (c,a,p)	X			X 		
NM Bone Scans	X			X 		

Examination	Screening 	C1D1 	C(2+)D1 	PSA Progression Confirmation 	End of Treatment 	Follow-up 
Rucaparib administration 		X	X			
Blood for Correlative Studies 	X		X 	X 	X 	
Urine for Correlative Studies 	X		X 	X 	X 	
Archival Tissue for Correlative Studies 	X					
BRCAness Test 	X					
Optional biopsy 				X		
Survival Follow-up						X

1. All Pre-study/Screening procedures should be completed within 4 weeks of study enrollment. CT Scan and NM Bone scan do not need to be repeated if done within preceding 90 days of visit.
2. C1D1 procedures do not need to be repeated if screening procedures have been done within 7 days of start of treatment.
3. Cycles will continue at  $28 \pm 3$  days according to criteria in [Section 6.4](#).
4. Confirmation of BRCAness by previous result or prospective analysis of archival tissue or blood sample biopsy. If archival tissue is unavailable, a new biopsy will NOT be required.
5. Hematology includes CBC with differential and platelets.
6. Chemistry includes Albumin, Alkaline Phosphatase, Aspartate Aminotransferase, Alanine Aminotransferase, Total Bilirubin, Calcium, Carbon Dioxide, Creatinine, Chloride, Glucose, Potassium, Protein, Sodium, and Urea Nitrogen.
7. Lipid panel to consist of cholesterol, triglycerides, LDL cholesterol HDL Cholesterol, VLDL, and non-HDL Cholesterol.
8. If treatment is discontinued prior to PSA progression, PSA testing will continue throughout follow-up until PSA progression or start of another treatment. Patients who have PSA progression prior to discontinuing treatment do not need to have PSA testing performed during follow-up.
9. Rucaparib will be administered as described in Section 6.
10. Blood collection for biomarkers will be collected at screening, C3D1, C7D1, and confirmed PSA disease progression ( $\pm 7$  days), if applicable, or at EOT visit (whichever occurs first).

11. For patients enrolled with an intact prostate, urine collection for biomarkers will be collected at screening, C3D1, C7D1, and confirmed PSA disease progression ( $\pm$  7 days), if applicable, or at EOT visit (whichever occurs first).
12. Archival tissue will be collected at screening (if available). Archival tissue should not be cut until instructed by the central lab.
13. Genomic or genetic testing for 'BRCAness' will be confirmed with either blood or tissue based testing.
14. An optional fresh tissue biopsy may be obtained at PSA Progression Confirmation Visit ( $\pm$  28 days) for subjects with radiographic disease progression.
15. CT scans of the chest/abdomen and pelvis and NM bone scans will be done at the time of PSA Progression Confirmation Visit ( $\pm$  28 days) as defined in section 10.1.
16. Follow-up should occur every 90 days ( $\pm$  14 days) for 2 years following End of Treatment as per standard of care (section 9).
17. Coagulation Panel includes PT/INR, PTT.
18. The end of treatment visit should occur within +/-3 days of the decision to discontinue treatment. If this visit overlaps with a regularly scheduled visit, only the procedures listed in the calendar for the EOT visit will be performed.
19. To be performed only if the subject has completed hormone therapy. Screening testosterone may be performed within 84 days of study enrollment.
20. Only patients who have suspected PSA progression during a regular study visit will have testing to confirm PSA progression at their next regularly scheduled visit. **Before continuation of treatment after confirmed PSA progression, the patient must agree to sign the Treatment After Progression Informed Consent Form.** Patients may complete the assessments required for PSA progression in conjunction with the next regularly scheduled cycle visit or at EOT.

## 9 STUDY PROCEDURES

### 9.1 Screening

- Informed Consent
- Physical exam (including weight and vital signs)
- Review of medical history/baseline symptoms
- Confirmation of BRCAness by previous result or prospective analysis of archival tissue or blood sample biopsy. If archival tissue is unavailable, a new biopsy will NOT be required
- 12-lead ECG (if medically indicated)
- ECOG Performance status
- Laboratory assessments:
  - Complete Blood Count (CBC) with differential (w/diff)
  - Complete Metabolic Panel (CMP) to include Albumin, Alkaline Phosphatase, Aspartate Aminotransferase, Alanine Aminotransferase, Total Bilirubin, Calcium, Carbon Dioxide, Creatinine, Chloride, Glucose, Potassium, Protein, Sodium, and Urea Nitrogen (fasting is not required)
  - Coagulation to include PT, PTT, INR
  - Lipid Panel to include cholesterol, triglycerides, LDL cholesterol HDL Cholesterol, VLDL and non-HDL Cholesterol (fasting not required)
  - PSA
  - Testosterone (for subjects who have previously been treated with hormone therapy)
- Blood collection for correlative studies (see Section 14.1.1 for details)
- Urine collection for correlative studies. Prior to collection of the urine specimen, a prostate exam will be performed by the treating physician (see Section 14.1.2 for details)
- Archival tissue collection for correlative studies (see Section 14.1.3 for details)

### 9.2 On-Treatment Evaluations (Day 1 of each cycle)

- Physical Exam (including weight and vital signs)
- ECOG Performance Status
- Laboratory assessments (do not need to be repeated at C1D1 if screening labs were performed within 7 days prior to treatment initiation):
  - CBC w/diff
  - CMP as defined in Section 9.1
  - Lipid Panel as defined in Section 9.1
  - PSA
- Blood collection for biomarkers at C3D1 and C7D1 (see Section 14.1.1 for details)
- Urine collection for biomarkers at C3D1 and C7D1. Prior to collection of the urine specimen, a prostate exam will be performed by the treating physician (see Section 14.1.2 for details).

- Safety assessment: monitoring and recording all adverse events and serious adverse events using the CTCAE version 5.0
- Review of concomitant medications
- Study drug administration & patient resupply (enough to last until Day 1 of the next treatment cycle).

### **9.3 PSA Progression Confirmation Visit**

Only for patients who have suspected PSA Progression at one of their regularly scheduled visits. Before continuation of treatment after confirmed PSA progression, the patient must agree to sign the Treatment After Progression Informed Consent Form. Patients may complete the assessments required for PSA progression in conjunction with the next regularly scheduled cycle visit or EOT Informed consent to treatment beyond PSA Progression

- Physical Exam (including weight and vital signs)
- ECOG Performance Status
- Laboratory assessments
  - CBC w/diff
  - CMP as defined in Section 9.1
  - Lipid Panel as defined in Section 9.1
  - PSA
- Blood collection for biomarkers ( $\pm$  28 days) (see Section 14.1.1 for details)
- Urine collection for biomarkers  $\pm$  28 days). . Prior to collection of the urine specimen, a prostate exam will be performed by the treating physician (see Section 14.1.2 for details).
- Safety assessment: monitoring and recording all adverse events and serious adverse events using the CTCAE version 5.0
- Review of concomitant medications
- CT scans of the chest abdomen and pelvis ( $\pm$  28 days)
- Nuclear Medicine (NM) Bone Scan ( $\pm$  28 days)
- Optional biopsy ( $\pm$  28 days) only for subjects who demonstrate radiographic progression. See Section 14.1.3 for details

### **9.4 End of Treatment**

- Physical Exam (including weight and vital signs)
- ECOG Performance Status
- Laboratory assessments:
  - CBC w/diff
  - CMP as defined in Section 9.1
  - Lipid Panel as defined in Section 9.1
  - PSA
- Blood collection for biomarkers ( $\pm$  28 days) (see Section 14.1.1 for details). (At confirmed PSA progression or EOT, whichever comes first).

- Urine collection for biomarkers  $\pm$  28 days). Prior to collection of the urine specimen, a prostate exam will be performed by the treating physician (see Section 14.1.2 for details). (At confirmed PSA progression or EOT, whichever comes first).
- Safety assessment: monitoring and recording all adverse events and serious adverse events using the CTCAE version 5.0
- Review of concomitant medications

## **9.5 Follow-up Evaluations Q 90 days ( $\pm$ 14 days)**

Survival follow-up, including survival status and post-study treatments. Follow-up may be conducted via phone call or record review if laboratory assessments are not required.

- Laboratory assessments:
  - If treatment is discontinued prior to PSA progression, PSA testing will continue throughout follow-up until PSA progression or start of another treatment. Patients who have PSA progression prior to discontinuing treatment do not need to have PSA testing performed during follow-up.

# **10 CRITERIA FOR EVALUATION AND ENDPOINT**

## **10.1 Efficacy**

Patients must receive one full cycle of rucaparib and have PSA assessed after that cycle to be evaluable for efficacy. Patients who do not meet evaluable criteria will be replaced.

PSA levels will be monitored monthly while on treatment for comparison to baseline levels with the objective of assessing the proportion of patients with a 50% reduction in PSA levels (PSA50).

PSA progression-free survival (PSA-PFS) is defined as the time from study enrollment until the time of PSA progression as defined by PCWG3 criteria or death.

Patients who start another anti-cancer treatment prior to PSA progression or who complete one year of follow-up without PSA progression will have their data censored at that time point.

Overall survival is defined as the time from study enrollment until death. Survival will be monitored while on study and every 90 days for 2 years after study discontinuation.

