Reference therapy	None
Statistical Methodology	
Primary Objective: The total sample size is 15 patients. The null hypothesis is that median PSA-PFS is 3 months. With an alternative hypothesis that median PSA-PFS is 12 months, a sample size of 15 provides 90% power at one-sided alpha = 0.05. The proportion of subjects who achieve PSA50 will be reported along with a 95% exact binomial confidence interval.
 
Descriptive analysis methods will be used to analyze tabulated safety characteristics. Kaplan-Meier methods will be used to assess the proportion of patients with an undetectable PSA after initiation of PARP therapy.

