### 1.2 Secondary Objectives and Endpoint

1.2.1 To assess the safety of rucaparib in patients with biochemically recurrent hormone-sensitive prostate cancer.

Endpoint: adverse events will be monitored regularly during patient enrollment and follow up to assess the toxicity of rucaparib using validated CTCAE v5.0 criteria.

1.2.2 To assess the proportion of patients with a 50% reduction in PSA levels (PSA50) compared to the baseline value at the time of study enrollment.

Endpoint: the levels of PSA will be monitored monthly for comparison to baseline levels.

1.2.3 To assess the proportion of patients with an undetectable PSA after initiation of PARP therapy at 6 and 12 months.

Endpoint: the levels of PSA will be monitored monthly for comparison to baseline levels to determine when PSA becomes undetectable.

1.2.4 To evaluate overall survival (OS) in nonmetastatic hormone-sensitive prostate cancer patients treated with rucaparib.

Endpoint: Subjects will be evaluated for survival using Kaplan-Meier estimation.

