### 4.2 Number of Patients

15 evaluable subjects will be enrolled.

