### **11.2 Secondary Objectives**

Descriptive analysis methods will be used to analyze tabulated safety characteristics. Kaplan-Meier methods and associated confidence intervals will also be used to analyze PSA progression-free survival and OS. The proportion of subjects who achieve PSA50 will be reported along with a 95% confidence interval. The proportion of subjects with an undetectable PSA after initiation of PARP therapy at 6 and 12 months will be assessed using Kaplan-Meier methods and associated confidence intervals. The proportion of subjects who exhibit an objective response will be reported along with an exact binomial confidence interval.

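### Section 10.1 replaces treated men who lack a full cycle 1 and a later PSA, and no all-treated efficacy set is defined, so PSA50 and PSA-PFS rest on a group selected after the first dose

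*Combined protocol and SAP*

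**What the plan says.** Section 10.1 sets the only efficacy population rule in the protocol: "Patients must receive one full cycle of rucaparib and have PSA assessed after that cycle to be evaluable for efficacy". It continues: "Patients who do not meet evaluable criteria will be replaced". Section 4.2 matches this: "15 evaluable subjects will be enrolled". Section 11 names no analysis population, no all-treated set and no sensitivity analysis that brings the replaced men back.

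The endpoints themselves are worded for patients or subjects in general. Section 1.2 states the aim as "To assess the proportion of patients with a 50% reduction in PSA levels (PSA50) compared to the baseline value", and the Study Summary says "The proportion of subjects who achieve PSA50 will be reported along with a 95% exact binomial confidence interval". Neither gives a denominator. Section 10.1 ties PSA50 to PSA taken during therapy: "PSA levels will be monitored monthly while on treatment for comparison to baseline levels". Section 11.2 adds: "The proportion of subjects with an undetectable PSA after initiation of PARP therapy at 6 and 12 months will be assessed using Kaplan-Meier methods".

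Section 10.1 counts death as a PSA-PFS event and censors at one year of follow-up without progression, or when another anti-cancer treatment is started. A man who stops early still has a PSA due at the end-of-treatment visit (Section 9.4). If he has not progressed, his PSA testing continues in follow-up, with visits every 90 days, until progression or another treatment (Section 9.5 and note 8 of the Section 8 calendar).

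**The concern.** Whether a man enters the efficacy analysis depends on what happens to him after he starts rucaparib. Someone who stops in cycle 1, or finishes it without a later PSA, leaves the denominator and another man takes his place. If such men do worse than those who stay, the estimates describe a favourable subset. There is no control arm in which the same selection would occur, so the published PSA50 proportion would be taken at face value.

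Two kinds of PSA-PFS event can also disappear. A cycle-1 death is an event by definition, yet the man is not evaluable. A man who stops in cycle 1 and progresses later, while still being tested in follow-up, is lost as well.

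PSA50 is secondary and descriptive, and no decision rule hangs on it. What is at stake is the accuracy of the reported estimates and whether a reader can see who was left out.

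**Working it through.** **Inputs from the documents.** 15 evaluable men (Section 4.2); exponential PSA-PFS with a median of 12 months under the alternative (Section 11.1); censoring at one year (Section 10.1); an exact 95% interval for PSA50 (Study Summary).

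**Assumed inputs.** The documents give neither a PSA50 rate nor a cycle-1 dropout rate, so there is no plan figure for PSA50 to reproduce. I take 6 responders among 15 evaluable men and k = 1, 2 or 3 replaced men.

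**Step 1: PSA50.** If the replaced men respond at rate q, the all-treated proportion is (6 + kq)/(15 + k). The difference between the evaluable and all-treated proportions is f × (pE − pN), where f = k/(15 + k) is the replaced share of treated men and pE and pN are the response rates in evaluable and replaced men.

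| k | f | q = 0 (exact 95% CI) | q = 20% | q = 40% |
|---|---|---|---|---|
| 0 | 0 | 6/15 = 40.0% (16.3 to 67.7) | – | – |
| 1 | 6.3% | 6/16 = 37.5% (15.2 to 64.6) | 38.8% | 40.0% |
| 2 | 11.8% | 6/17 = 35.3% (14.2 to 61.7) | 37.6% | 40.0% |
| 3 | 16.7% | 6/18 = 33.3% (13.3 to 59.0) | 36.7% | 40.0% |

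The largest shift is 40.0 − 33.3 = 6.7 points, against an interval width of 67.7 − 16.3 = 51.4 points. The sign can reverse: if one replaced man had responded, the all-treated figure would be 7/16 = 43.8%, and 40% would be too low.

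**Step 2: undetectable PSA by Kaplan-Meier.** Assume events at months 2, 3, 4, 5, 6 and 8 among 15 men, then add 3 early leavers. The 12-month figure is 6/15 = 40.0% without them.

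- Leavers censored at month 1, before any event: still 40.0%.
- Leavers censored at month 4: 1 − (15/18) × (9/12) = 37.5%.
- Leavers followed event-free to month 12: 6/18 = 33.3%.

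**Step 3: PSA-PFS.** Under the alternative the hazard is ln 2/12 = 0.0578 per month. Over 12 months, 15 men give 15 × 0.5 = 7.5 expected events and 7.5/0.0578 = 129.8 person-months. The median is ln 2 × 129.8/7.5 = 12.0 months, which recovers the plan's figure. Adding excluded men:

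- One death at month 0.5: ln 2 × 130.3/8.5 = 10.6 months.
- One progression at month 6: ln 2 × 135.8/8.5 = 11.1 months.
- Three progressions at month 6: ln 2 × 147.8/10.5 = 9.8 months.

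**Step 4: could those later progressions be seen?** Appendix B does not let a PSA rise in the first 12 weeks (84 days) count as progression. That delays progression and does not prevent it. The first follow-up visit is nominally 90 days after end of treatment, and testing continues from there, so a later progression in an early leaver is observable under the existing schedule.

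**The case against.** Evaluable-only analysis with replacement is declared in advance here and enrolment is sized on it. Activity in men who received a full cycle is a legitimate phase II question. A man who takes a few days of drug has little chance of showing a 50% fall at an end-of-treatment PSA, so counting him as a non-responder answers a different question. Counting a missing PSA as non-response also pulls the estimate down. All of that stands, and it is why the evaluable result should be kept and the all-treated result set beside it.

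The denominator is also inferred: Section 11 never states it. That stands too, but Section 10.1 is the only efficacy population rule, and the inference is the natural one. The small shift relative to the interval is true as well, although the interval measures sampling error and does not account for selection.

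Three other readings are tempting and go beyond the documents.

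- That PSA50 is biased upward. The direction depends on how the replaced men respond, and the documents say nothing about that or about how many there will be.
- That the primary test is undermined. Section 11.1 does not name the test, and the assumed medians of 9.8 to 11.1 months remain far above the null of 3 months.
- That the 12-week rule confines the PSA-PFS loss to cycle-1 deaths. Step 4 shows that later progressions are lost too.

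Nor is the number treated hidden. Adverse events are collected from the first dose (Section 15.4.1), so it should appear in the safety tables. What the plan does not require is the number replaced, the reasons, or those men's PSA results.

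**Conclusion.** The concern holds in conditional form. The efficacy set depends on events after the first dose, and no all-treated analysis is planned to show the effect. PSA50 is overstated, unchanged or understated according to whether the replaced men respond less often, equally often or more often than the rest. With nobody replaced there is no effect.

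In the cases assumed here, up to 3 replaced non-responders lower PSA50 by at most 6.7 points. For PSA-PFS, one to three excluded events lower a 12.0-month median by about 1 to 2 months. These sizes rest on an assumed number of replaced men, an assumed 6 responders and assumed event times; none can be fixed from the documents. This is an improvement worth making at low cost, not a defect that invalidates the design.

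**What to change.** In Sections 10.1 and 11:

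1. Report PSA50 with its exact interval for every man who takes at least one dose, alongside the evaluable-set result. Use on-treatment and end-of-treatment PSA only, in keeping with Section 10.1, and count a man with no qualifying PSA as a non-responder.
2. Report PSA-PFS and undetectable PSA in the same all-treated set, using the PSA already due at end of treatment and in follow-up. Keep the plan's censoring rules and count cycle-1 deaths as PSA-PFS events. State how Appendix B's progression definition applies to a man whose PSA never fell below baseline, because its numeric threshold is written only for a rise after a decline.
3. Keep 15 evaluable men as the enrolment target.
4. Report the number treated, the number replaced and the reasons.

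The cost is a short amendment with no new visits, samples or change of target; the Appendix B clarification is the part that needs thought. PSA50 may come out slightly lower, and slightly too low where a PSA is missing for administrative reasons. Progression in early leavers will be dated less precisely. With visits every 90 days in place of 28, and a rise equally likely at any time between visits, the first qualifying value is found on average 45 − 14 = 31 days later. Confirmation then waits for the next visit, and some of these men may start another treatment and be censored first.

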We hypothesize that treatment with PARP inhibitor monotherapy in men with high risk biochemically recurrent prostate cancer (i.e., PSA only relapse with no radiographic evidence of disease with a PSA doubling time of  $< 9$  months) will result in acceptable disease control in terms of PSA response, allow delay of androgen deprivation therapy, and delay the onset of metastasis.

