#### **4.4 Study Duration**

Expected enrollment duration is 12 months, patients will remain on study treatment until PSA progression defined by PCWG3 (unless they meet the criteria for continued treatment outlined in section 6.4.1), with 2 years of follow up after study treatment. We anticipate a total of 2-3 years until completion of the clinical trial.

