# **11 STATISTICAL CONSIDERATIONS**

### **11.1 Primary Objective**

The total sample size is 15 patients. The null hypothesis is that median PSA-PFS is 3 months. With an alternative hypothesis that median PSA-PFS is 12 months, and assuming PSA-PFS is exponentially distributed, a sample size of 15 provides 90% power at one-sided alpha = 0.05. The median progression-free survival in the PROfound trial of olaparib treated patients was 7.4 months for Arm A (ie patients with BRCA1, BRCA2 or ATM alterations). This trial evaluated patients who's cancer was highly refractory and had more advanced disease. The median PFS in the TOPARP-A trial was 9.8 months in biomarker selected patients. In the ROAR trial, the patients have early disease which is hypothesized to be more responsive to treatment. We hypothesize that the median PFS will be longer than that observed in prior studies where olaparib was tested in a more advanced setting.

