### **PSA Progression**

PSA should be monitored at the beginning of every cycle. Any rise in PSA during the first 12 weeks of treatment should be monitored but should not be deemed evidence of progression. Record the percent change from baseline at 12 weeks. After a decline from baseline: record time from start of therapy to first PSA increase that is  $\geq 25\%$  and  $\geq 2$  ng/mL above the nadir, and which is confirmed by a second value  $\geq 3$  weeks later (i.e., a confirmed rising trend).

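### Censoring PSA-PFS at the start of another anti-cancer treatment is likely informative and likely biases the primary endpoint upwards, by an amount the plan does not examine

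*Combined protocol and SAP*

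**What the plan says.** Section 10.1 defines PSA-PFS as the time from enrolment to PCWG3 PSA progression or death. New therapy is not an event. Two groups are censored: "Patients who start another anti-cancer treatment prior to PSA progression", and men who reach one year of follow-up without progression.

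Appendix B (PSA Progression) requires a rise of at least 25% and at least 2 ng/mL above the nadir, "and which is confirmed by a second value" taken at least 3 weeks later. A rise in the first 12 weeks is monitored but is not progression.

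For men who stop rucaparib before progression, section 9.5 and note 8 of the Study Calendar continue PSA testing only until progression or the start of another treatment. Follow-up visits are every 90 days (± 14), and post-study treatments are recorded there.

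Section 11.1 sets the test against a fixed reference: "The null hypothesis is that median PSA-PFS is 3 months". Section 11.2 analyses PSA-PFS by Kaplan-Meier with confidence intervals. Sections 11.1 to 11.3 contain no sensitivity or competing-event analysis for the censoring rule.

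**The concern.** Kaplan-Meier treats a censored man as having the same future risk as the men still followed. That is doubtful if he switched because his PSA was rising. Every man enters with a rising PSA and no metastases on conventional imaging. PSA is the only disease marker measured at every cycle, and scans after screening are scheduled only around the PSA Progression Confirmation Visit. A man can therefore start another treatment after a first qualifying rise that is not yet confirmed, or during an early rise that the endpoint ignores. In either case a probable failure is entered as a censored time, and his later confirmed progression is never observed.

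The timing of androgen deprivation therapy (ADT) matters to the trial's purpose. Section 2 hypothesises that treatment will "allow delay of androgen deprivation therapy, and delay the onset of metastasis". An early start of ADT is thus close to a failure of that aim, yet the primary endpoint does not count it.

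With a single arm of 15 and a fixed 3-month null, there is no control group in which the same censoring could offset the effect. Each failure lost to censoring lowers the event count and makes rejection easier.

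**Working it through.** **Inputs from the documents.** n = 15, null median 3 months, alternative median 12 months, exponential times, one-sided alpha 0.05 (section 11.1); censoring at 12 months (section 10.1); 12-month accrual (section 4.4).

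**Assumed, because the documents do not give them.** The test (one-sample log-rank), the share q of would-be progressors censored by a switch (10% to 30%), and how long before progression they switch (0, 1 or 2 months).

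**The plan's own figure.** Section 11.1 states that "a sample size of 15 provides 90% power at one-sided alpha = 0.05". With one year of follow-up per man, expected events at a 12-month median are d = 15 × (1 − 2^(−12/12)) = 7.5. For a one-sample exponential log-hazard test, power = Φ(√7.5 × ln(12/3) − 1.645) = Φ(3.797 − 1.645) = 98.4%. The stated 90% is not reproduced. It is approached by 12-month accrual with no added follow-up (4.2 events, 88.3%), which conflicts with the one-year follow-up, or by a normal-approximation test of the 3-month proportion (91.3%). Under the stated follow-up 90% is conservative, and nothing below depends on it.

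**Apparent median.** If a random share q of progressors is censored at the moment of progression, the observed event hazard is (1 − q) times the true hazard, so the apparent median is the true median ÷ (1 − q). At a true median of 3 months:

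- q = 10%: 3 ÷ 0.9 = 3.3 months
- q = 20%: 3 ÷ 0.8 = 3.75 months
- q = 30%: 3 ÷ 0.7 = 4.3 months

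**Type I error.** Simulated trials with n = 15, a true median of 3 months and 12-month censoring; the test rejects when (O − E)/√E is below −1.645, where O is observed events and E is expected events under the null:

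| Share switching | Switch at progression | 1 month earlier | 2 months earlier |
|---|---|---|---|
| 0% | about 4% | about 4% | about 4% |
| 10% | 8% | 7% | 6% |
| 20% (3 of 15 men) | 16% | 12% | 10% |
| 30% | 27% | 21% | 16% |

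Counting the switch as an event keeps the rate at about 3.5% when men switch at progression and at 2% to 3% when they switch a month earlier.

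**Dependence on the test.** If the decision is instead that the lower limit for the Kaplan-Meier median exceeds 3 months, and men switch at progression, the rate goes from 1.6% with no switching to 4.2%, 8.1% and 13.1% at q = 10%, 20% and 30%.

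**The 12-week rule.** Twelve weeks is 84 ÷ 30.44 = 2.76 months. With an exponential median of 3 months, 1 − 2^(−2.76/3) = 47% of failures fall in the period when a rise cannot count. The table does not model this. Moving those failures to week 12 gives a type I error of about 8% with no switching at all, so the 4% baseline describes the simple exponential model rather than the endpoint as written.

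**The case against.** The strongest reply is that a man who follows the plan will usually have confirmed progression before he switches.

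- Note 20 of the Study Calendar places confirmation at the next regular visit, so the on-treatment window is about one 28-day cycle.
- PSA is measured at the end-of-treatment visit, and the confirmation assessments may be done there.
- An unconfirmed rise is not a listed reason for stopping in section 6.4.2.
- The Study Summary excludes ADT and androgen-receptor agents during the study period, and section 6.4.1 lets some men continue rucaparib after progression.
- PSA testing continues off treatment until another treatment starts.

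These features narrow the window but do not close it. Men may withdraw at any time, and a man who stops rucaparib and starts ADT is censored. Section 6.4.1 applies only once progression is shown. Off treatment, the interval between PSA tests is about 90 days. The 12-week rule lies outside the confirmation argument altogether.

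Three stronger readings are tempting, and the documents support none of them.

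- A reader might infer that men start ADT because PSA is rising and that PSA-PFS is therefore biased. No section gives a reason or a rate for switching, and a switch for toxicity with controlled PSA need not bias upwards.
- A reader might take 27% as the false-positive rate. It is the upper end of a scenario: an assumed share of 30%, an assumed test, and every switch exactly at progression.
- A reader might conclude that nothing can be recovered. Confirmed progression after the switch is indeed lost, but the first rise and the new treatment are on record.

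**Conclusion.** The point stands in a limited form. As written, the rule can turn PSA failures into censored times, and no planned analysis would show whether it had. The likely direction is upwards, to the extent that switches are prompted by rising PSA. That motive is a reasonable inference from the population and the visit schedule, not a statement in the documents.

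The size is unknown. For an assumed 10% to 30% of would-be progressors, type I error at the 3-month null rises from about 4% to 8% to 27% with switching at progression, and to about 6% to 16% with switching two months earlier. It is lower with a test based on the Kaplan-Meier lower limit. If few men switch before confirmation, the effect is small. Because three men are already 20% of the sample, the sponsor should plan the check in advance.

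**What to change.** Keep the censoring rule as the primary analysis and add the following to sections 10.1 and 11.1:

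- **(a)** A sensitivity analysis in which the start of any other anti-cancer treatment before confirmed progression is an event on its start date. Present it as a conservative bound, because it also counts switches for toxicity with controlled PSA as failures.
- **(b)** A second analysis in which new treatment after an unconfirmed rise meeting the 25% and 2 ng/mL thresholds, including a rise in the first 12 weeks, is progression on the date of that rise. State the reference value for a man whose PSA has not fallen, because Appendix B words the thresholds only for a rise after a decline.
- **(c)** A listing of the number, timing, reason and last PSA of men censored for new treatment.

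Monthly PSA and post-study treatments are already collected, and the current rule already needs the start date of new treatment. The reason for switching is not named in section 9.5 and may need one added form item. The cost is a few lines of text, a little more analysis, and a less favourable second estimate beside the primary one, with (a) possibly biased downwards. No treatment rule or visit changes.
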